3. STUDY DESIGN

3.1. Study Overview

This is a Phase 1/2a, open-label, multi-center, non-randomized, multiple dose, safety, tolerability, pharmacokinetic, and pharmacodynamic study of PF-06873600 administered as a single agent in sequential dose levels and then in combination with endocrine therapy. In Part IA, successive cohorts of patients will receive escalating doses of PF-06873600 starting at 1 mg BID dosed on a continuous basis and then in dose finding (Part IB) with immediate release formulations of PF-06873600 in combination with endocrine therapy (ET) in an outpatient setting. In Part IC, successive cohorts of patients will receive escalating doses of PF-06873600 testing a modified release (MR) formulation in a MR cohort evaluation and then in dose finding (Part IB) with modified release formulations of PF-06873600 in combination with endocrine therapy (ET) in an outpatient setting.

This study contains 2 parts, dose escalation with single agent (Part IA and IC) and then dose finding with PF-06873600 in combination with endocrine therapy (letrozole and fulvestrant, independently with both immediate and modified release formulations) (Part IB) followed by dose expansion arms in combination with endocrine therapy (Part 2). The decision to initiate Part 2 with either the immediate release formulation or the modified release formulation will

be made following a careful review of all available data from Part 1 (1A, 1B, and 1C) and in consultation with the C3661001 Safety Team.

The Japan lead-in cohort (J-LIC) will be added separately as a sub-cohort in order to assess the safety of monotherapy of PF-06873600 in Japanese population. Detailed information is provided in the [Appendix 7](#). Japanese participants will be able to enroll into Part 2 after safety and tolerability of monotherapy of PF-06873600 in Japanese participants is confirmed.

The overall study design is depicted in Figure 8 below.

Figure 8. Overall Study Schema

[figure not shown]
[figure not shown]

Figure 9. Modified Release Selection Cohort Study Schema (within Part 1C through Cycle 1):

Part 1A will estimate the maximum tolerated dose/recommended Phase 2 dose/recommended dose for expansion (MTD/RDE) in sequential dose escalation safety cohorts for PF-06873600 as a single agent in women of any menopausal status and men with HR-positive HER2-negative advanced or mBC (third or fourth line setting) and in women/men with locally recurrent/advanced or metastatic TNBC and women with advanced platinum resistant ovarian cancer.

Any given PF-06873600 dose in Part 1A (or Part 1C) may be escalated or de-escalated at full or intermediate dose levels, depending on emerging clinical data. Parallel biomarker cohorts may be initiated for HR-positive HER2-negative advanced or mBC patients only, once the respective preceding dose escalation safety cohort has cleared (see [Section 3.1.1](#)).

After the MTD/RDE for PF-06873600 as a single agent has been identified in Part 1A (or Part 1C) based on safety and clinical observations, initiation of combination dose de-escalation with PF-06873600 in combination with letrozole and PF-06873600 in combination with fulvestrant independently (Part 1B) will be initiated at the single agent MTD or RDE in women of any menopausal status with HR-positive HER2-negative advanced or mBC. In Part 1B, the PF-06873600 dose can be de-escalated at full or intermediate dose levels. In addition both available formulations of PF-06873600 at the respective RDE will be studied in combination with endocrine therapy in Part 1B. Approximately 12 patients will be dosed in the respective endocrine therapy combinations, with approximately 6 patients receiving PF-06873600 IR + endocrine therapy and approximately 6 patients receiving PF-06873600 MR + endocrine therapy in both the fulvestrant and letrozole arms.

Part 2 will evaluate the dose selected (RDE) in combination with endocrine therapy (letrozole and fulvestrant in independent dose expansion arms) depending on clinical observations from Part 1B (See [Section 3.2](#)).

PF-06873600 will initially be administered orally BID on a continuous basis. If emerging PK data from initial dose levels in Part 1A (or Part 1C), demonstrate the feasibility of once daily (QD) dosing, the dose escalation may continue with QD dosing, following the dose escalation schema with the same total daily dose as planned for BID dosing. The evaluation of an alternative dosing regimen (eg, QD) may be considered during the course of dose escalation or after determination of the MTD for the BID regimen based on emerging and available preliminary clinical data, including safety/tolerability, laboratory, PK and PD findings. If an alternative dosing regimen (eg, QD) assessment occurs after determining the MTD of the BID regimen, it will be initiated with a dose level at a comparable total daily dose determined from the MTD of the BID regimen.

Intermittently administered PF-06873600 dosing schedules may also be evaluated if indicated based on emerging clinical data. As an option, PF-06873600 may be administered continuously for three weeks followed by one week off if indicated by emerging clinical safety and PK data.

All cycles are 28 days in length and treatment will continue until progression of disease, uncontrollable toxicity, a decision by the patient or investigator to discontinue treatment or the study is terminated. Patients experiencing toxicity including a dose limiting toxicity (DLT) may be managed with dose modification or discontinuation from treatment. The proposed doses, schedule(s) and PK time points may be reconsidered and amended during the study based on the emerging safety and PK data.

The time on study can vary depending on the observed toxicity and potential benefit an individual patient derives. It is estimated that each patient may remain on treatment for approximately 6-8 cycles, making total study duration approximately 32-36 weeks. Actual duration can be longer, if a patient derives benefit from study treatment.

Approximately 75 patients are expected to be enrolled in the dose escalation/finding safety cohorts and an additional 6-12 patients are expected in the biomarker cohorts in Parts 1A and 1C. The actual number of patients enrolled will depend on the tolerability of PF-06873600 and the number of dose levels required to identify the MTD/RDE. Approximately 100 patients are expected to be enrolled in Part 2.

3.1.1. Part 1A PF-06873600 Single Agent Dose Escalation

Part 1A consists of single agent dose escalation in dose escalation safety cohorts as well as biomarker cohorts. The dose escalation safety cohorts will be initiated in 1-2 patients for the first 2 planned dose levels starting at 1 mg BID orally on a continuous basis and dose escalation will proceed according to the modified toxicity probability interval (mTPI) method. When a dose level is deemed safe following a DLT observation period of 28 days and based on the discussion by the safety review team (comprised of the Investigators and the Sponsor), dose escalation will occur to the next dose level ([Table 2](#)).

While patients enrolled in the dose escalation safety cohorts are being evaluated, patients may enroll into additional biomarker cohorts (approximately 6 patients in each cohort) requiring mandatory pre- and -on treatment tumor and skin biopsies. An end of treatment tumor biopsy is optional but encouraged. Initiation of enrollment into the first biomarker cohort will be based on observations of key pharmacodynamic (PD) findings (eg, neutropenia, gastrointestinal toxicities, and/or other PK/PD markers) and/or reaching a predicted active dose (noted in Figure 8 as §Biomarker Cohort). Enrollment into a biomarker cohort can occur after the dose level is deemed safe for escalation to a higher dose level or at the MTD. Biomarker cohorts will enroll women and men with HR-positive HER2-negative advanced or mBC. Because these additional patients will receive a dose lower than the concurrent dose escalation safety cohort or will be enrolled at a dose following the DLT evaluation period in the first 2-4 dose escalation safety cohort patients enrolled, their potential DLT observations may not be strictly used in the mTPI method for the ongoing dose finding. However, the safety profile from these additional patients will be used to establish the MTD or RDE.

3.1.2. Part 1B PF-06873600 Dose Finding in Combination with Endocrine Therapy

After the single-agent PF-06873600 MTD/RDE has been determined for both the IR and MR formulations, enrollment will be initiated into Part 1B which will evaluate the PF-06873600 in combination with letrozole and in combination with fulvestrant in independent cohorts in women with HR-positive HER2-negative advanced or mBC. PF-06873600 will be administered orally on a continuous basis (unless the dose schedule has changed during Part 1A or Part 1C), while letrozole and fulvestrant will be administered per standard of care. Available safety and clinical data will be reviewed by the safety review team. The PF-06873600 dose in combination with letrozole may be decreased if determined to not be tolerable. The PF-06873600 dose de-escalation in combination with letrozole will follow the mTPI method. Similarly, the PF-06873600 dose in combination with fulvestrant may be decreased if determined to not be tolerable. The PF-06873600 dose de-escalated in combination with fulvestrant will follow the mTPI method. The MTD/RDE of each of the PF-06873600 formulations (IR and MR) in combination with the respective endocrine therapy (letrozole and fulvestrant) will be declared when at least 6 patients have been enrolled at a dose level that is predicted to be the MTD/RDE for each of the respective combination per the mTPI. Once the MTD/RDE of PF-06873600 in combination with letrozole and the MTD/RDE of PF-06873600 in combination with fulvestrant have been confirmed, a recommended dose for expansion for each combination will be declared and enrollment into Part 2 may be initiated. The decision to dose either the MR or IR or MR and IR formulation in Part 2 will be made following a careful review of all available clinical data and in alignment with C3661001 Safety Team.

Similar to Part 1A and/or Part 1C, dose escalation, all safety, PK and PD information from safety cohorts in Part 1B available will be used to determine the PF-06873600 MTD/RDE for the respective combination treatments.

3.1.3. Part 1C PF06873600 MR Formulation

“A MR formulation with two designed release rates shorter duration (eg, 6 -hour) and longer duration (eg, 12-hour) release, respectively, has been developed for PF-06873600 and were studied in the Part 1C MR Selection Cohort only.” Compared to the Immediate Release (IR) formulation, the MR formulation has the potential to achieve more prolonged effective target inhibition during a dose interval. Emerging pharmacokinetics and safety data for the IR formulation suggest there is a large peak-to-trough fluctuation in steady-state concentrations and that a lower maximal concentration (C_{max}) could potentially improve tolerability. Therefore, the MR formulation with the two release rates were evaluated in an MR selection cohort in this study.

The MR selection cohort enrolled 3 to 5 evaluable patients. These patients received two single doses of the MR formulation during a 7-day lead-in period (Day -7 to Day -1), prior to receiving the IR formulation of PF-06873600 twice daily in 28-day cycles. During the 7-day lead-in period, patients first received a single dose of the shorter release tablets on Day -7, and then another single dose of the longer release tablets on Day -4. The dose for the shorter and longer release MR tablets were administered during the lead-in period, as well as the IR dose administered starting from Cycle 1 Day 1, were no higher than the highest nominal dose tested found to be safe from the IR dose escalation. Serial PK sampling was performed for 24 hours following each of the MR formulation doses on Day -7 and Day -4, and for 12 hours following the IR formulation morning dose on Cycle 1 Day 1. PK was compared between the shorter and longer release MR tablets, and also between each of the two release rate MR tablets and IR. Based on the PK data from the MR selection cohort, 12-hour release rate provides a slower release compared to the 6-hour release rate, thus achieves more prolonged drug coverage during a dosing interval. Therefore, 12-hour release rate was selected to be further investigated during MR dose escalation.

The MR dose escalation, proceeded with one of the selected MR formulation release rates according to the mTPI method until a MTD/RDE is determined. The starting dose for the MR dose escalation was selected to achieve similar steady-state AUC during one dose interval ($AUC_{ss,\tau}$) as the highest safe IR dose based on prediction. The dose increment will be no more than a 50% increase. After MTD/RDE is determined, a biomarker cohort may be open to enroll patients with HR-positive HER2-negative advanced or mBC requiring mandatory pre- and on-treatment tumor and skin biopsies.

During the Part 1C dose escalation, all available safety, PK and PD information from dose escalation safety and biomarker cohorts in will be used to determine the PF-06873600 MTD/RDE as a single agent.

3.1.4. Starting Dose for Part 1A

The starting dose of PF-06873600 will be 1 mg administered orally BID on a continuous basis in 28 day cycles.

3.1.5. Criteria for Dose Escalation

Compared to the traditional mTPI method, the proposed mTPI method for this protocol includes stopping rules and dose escalation/finding criteria, which prevents the target DLT rate to reach $\geq 33\%$ for determining the MTD. This proposed mTPI method, targeting a DLT rate of 27.5% and an acceptable DLT interval (22.5% to 32.5%), will be utilized in Part 1 dose escalation/finding phase, and will also be used to monitor the DLTs so as not to cross toxicity boundaries in the expansion of a cohort. In this process, the upper limit of the DLT rate to determine a MTD will be $< 33\%$. This proposed mTPI method is more conservative than the traditional toxicity probability interval (TPI) method.

The mTPI method relies upon a statistical probability algorithm, calculated using all patients treated in the current dose level to determine one of the following dose-finding decisions: the subsequent dose should be escalated, maintained at the current dose, or de-escalated in the next cohort of 1-4 patients, or the trial should be terminated (Table 1).

Table 1. Dose Escalation/De-Escalation Decision Rules

DLT	n=2	n=3	n=4	n=5	n=6	n=7	n=8	n=9	n=10	n=11	n=12
0	E	E	E	E	E	E	E	E	E	E	E
1	S	S	S	S	E	E	E	E	E	E	E
2	D	D	D	S	S	S	S	S	S	S	E
3		U	U	D	D	S	S	S	S	S	S
4			U	U	U	U	D	S	S	S	S
5				U	U	U	U	U	D	S	S
6					U	U	U	U	U	U	U
7						U	U	U	U	U	U
8							U	U	U	U	U
9								U	U	U	U
10									U	U	U
11										U	U
12											U

Actions to be taken: D = De-escalate the dose; E = Escalate the dose; S = Stay at the dose. U = Unacceptable toxicity.

Initially, dose cohorts may consist of 1-2 patients in the single agent dose escalation in Part 1A. When a DLT is observed, additional patients will be enrolled and dose escalation decision will follow the mTPI criteria. Table 2 showing escalating doses with a 100% to 150% increase from the previous dose in dose levels (DLs). In later cohorts it is anticipated that total daily dose level increases may approximate 100% or less depending on emerging available clinical data, including safety/tolerability, laboratory, PK and PD findings.

The total daily dose will be administered once a day (QD) or in divided doses of either two (BID) or three times a day (TID).

Initial dose levels are provided in Table 2 and intermediate dose levels may be considered as indicated. Intra-patient dose escalation for patients enrolled in dose level 1 and 2 may be considered in consultation with the sponsor. Once the respective dose level has been declared safe, patients who have completed at least 2 Cycles of treatment at the original enrolled dose level may escalate to the next higher dose level that has cleared the DLT observation period of 28 days.

Table 2. PF-06873600 Dose Levels (Immediate Release Formulation)

DOSE LEVEL (DL)*	DOSE	TOTAL DAILY DOSE***
DL 1**	1 mg BID	2 mg
DL 2	2 mg BID	4 mg
DL 3	5 mg BID	10 mg
DL 4	10 mg BID	20 mg
DL 5 and Beyond		Escalation to continue to the MTD or desired pharmacological activity

*The proposed doses, schedule(s), and PK time points may be reconsidered or amended during the study based on the emerging safety and PK data. Intermediate doses may be considered when deemed necessary based on on-going evaluation of safety and toxicity data.

** Starting dose DL1.

*** Total daily dose may be administered in up to 3 divided doses.

In principle, all patients must be evaluated for a minimum DLT observation period of 28 days in Part 1. However, in order to be evaluable for DLT assessment patients need to have received at least 75% of planned doses unless the patient has experienced a DLT prior to receiving 75% of the planned dose.

The dose escalation in Part 1A, and 1C, dose finding in Part 1B, and each arm of the dose expansion in Part 2 of the study will stop as the applicable following criteria are met:

- The maximum sample size has been achieved (approximately 75 patients in Part 1, excluding patients enrolled in biomarker cohorts, and approximately 70 patients in Part 2);

- 6 to 12 evaluable patients (for Parts 1A, Part 1B, and Part 1C) that have been enrolled at a PF-06873600 dose level (as a single agent, in combination with letrozole, and in combination with fulvestrant, each) that is predicted to be the MTD per the mTPI method;
- All dose levels explored appear to be overly toxic, and the MTD cannot be determined.

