3.2. Part 2 PF-06873600 Combination Dose Expansion

Part 2 dose expansion is an open-label, multi-center, non-randomized study to assess the preliminary anti-tumor activity and the safety and tolerability of PF-06873600. PF-06873600 will be administered at the RDE in 28 days cycles in combination with endocrine therapy in two separate dose expansion arms. Patients may be treated with IR or MR formulations depending on emerging data from Part 1 and availability.

The single agent PF-06873600 RDE from Part 1A will be used to initiate the Part 2 dose expansion arm studies, which may be de-escalated, depending on emerging data if indicated. Additionally, the PF-06873600 RDE in combination with letrozole and PF-06873600 RDE in combination with fulvestrant from Part 1B will be used to initiate the Part 2 respective combination dose expansion arm studies, which may be de-escalated, depending on emerging data if indicated.

3.2.1. Part 2/Arm A- PF-06873600 in Combination with Fulvestrant in HR-Positive HER2-Negative Locally Advanced or mBC (Second- or Third-Line Setting)

PF-06873600 will be evaluated in combination with fulvestrant at the RDE in HR-positive HER2-negative advanced or mBC in patients who have received prior combined CDK4/6 inhibitor and a nonsteroidal aromatase inhibitor, and up to 1 prior line of chemotherapy. This expansion cohort will enroll approximately 40 patients.

3.2.2. Part 2/Arm B - PF-06873600 in Combination with Letrozole in HR-Positive HER2-Negative Locally Advanced or mBC (naïve to CDK4/6 inhibitors).

PF-06873600 will be evaluated in combination with letrozole at the RDE in HR-positive HER2-negative advanced or mBC in patients, with supportive available preliminary PF-06873600 clinical data. Patients who have not received any prior treatment with a CDK4/6 inhibitor in the advanced or metastatic setting (prior adjuvant therapy with AI is permitted) will be enrolled. This expansion cohort will enroll approximately 30 patients.

3.2.3. Part 2/Arm C- PF-06873600 in Combination with Fulvestrant in HR-Positive HER2-Negative Locally Advanced or mBC (naïve to CDK4/6 inhibitors)

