The mTPI design uses a Bayesian decision-theoretic framework and a beta/binomial hierarchical model to tailor dose-escalation and de-escalation decisions. These rules are conceptually similar to those used by the 3+3 design and all the dose-escalation decisions for a given trial can be pre-calculated under the mTPI design and presented in a two-way table.

The decision rules to "dose escalate" (E), "no change in dose" (S), "dose de-escalate" (D) or "dose de-escalate, unacceptable toxicity" (U) are described below:

Table 2 Dose Escalation Decision Rules

DLT	n=2	n=3	n=4	n=5	n=6	n=7	n=8	n=9	n=10	n=11	n=12
0	E	E	E	E	E	E	E	E	E	E	E
1	S	S	S	S	E	E	E	E	E	E	E
2	D	D	D	S	S	S	S	S	S	S	E
3		u	u	D	D	S	S	S	S	S	S
4			u	u	u	u	D	S	S	S	S
5				u	u	u	u	u	D	S	S
6					u	u	u	u	u	u	u
7						u	u	u	u	u	u
8							u	u	u	u	u
9								u	u	u	u
10									u	u	u
11										u	u
12											u

Actions to be taken: D = De-escalate the dose; E = Escalate the dose; S = Stay at the dose. U = Unacceptable toxicity.

In principle, all patients must be evaluated for a minimum DLT observation period of 28 days in both Part 1 and Part 2. However, in order to be evaluable for DLT assessment patients need to have received at least 75% of planned doses unless related to treatment emergent toxicity.

The dose escalation in Part 1A and 1C, dose finding in Part 1B, and each arm of the dose expansion in Part 2 of the study will stop as the applicable following criteria are met:

- The maximum sample size has been achieved (approximately 50 patients in Part 1, excluding patients enrolled in biomarker cohorts, and approximately 30 patients in each dose arm in Part 2);
- 6 to 12 evaluable patients (for Parts 1A, Part 1B and Part 1C) that have been enrolled at a PF-06873600 dose level (as a single agent, in combination with letrozole, and in combination with fulvestrant, each) that is predicted to be the MTD per the mTPI method;
- All dose levels explored appear to be overly toxic, and the MTD cannot be determined.

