4.2. Statistical Decision Rules

4.2.1. Part 1

Decision rules are based on calculating unit probability mass (UPM) of three dosing intervals corresponding to under, proper, and over dosing in terms of toxicity. Specifically, the underdosing interval is defined as $(0; J)T-e_1$, the over-dosing interval $(pr+e_2)$, and the proper-dosing interval $(pT-e_1, pr+e_2)$, where e_1 and e_2 are small fractions. For a target DLT rate of 0.275, the target equivalence interval is (0.225, 0.325). The three dosing intervals are associated with three different dose-escalation decisions (Table 1). The under-dosing interval corresponds to a dose escalation (E), over-dosing corresponds to a dose de-escalation (D), and proper-dosing corresponds to remaining at the current dose (S). Given a dosing interval and a probability distribution, the unit probability mass (UPM) is defined as the ratio of the probability of the interval to the length of the interval. Once the safety assessment is complete for Cycle 1 (ie, 28 days after the first dose), the focus will be on allocation of new subjects to the dose most likely to be an MTD.

The dose escalation in Part IA and JC, dose finding in Part JB, and each arm of the dose expansion in Part 2 of the study will stop as the applicable following criteria are met:

- *The maximum sample size has been achieved (approximately 75 patients in Part 1, excluding patients enrolled in biomarker cohorts, and approximately 70 patients in Part 2);*
- *6 to 12 evaluable patients (for Parts IA, Part 1B and Part 1C) that have been enrolled at a PF-06873600 dose level (as a single agent, in combination with letrozole, and in combination with fulvestrant, each) that is predicted to be the MTD per the mTPI method;*
- *All dose levels explored appear to be overly toxic, and the MTD cannot be determined.*

Specifically the mTPI approach formalizes stopping rules as follows:

Rule 1 (early termination): if the first dose is too toxic $\Pr(p_1 > PT | data) > \alpha$; $\alpha = 0.975$

Rule 2 (dose exclusion), if dose = i is too toxic $\Pr(p_i > PT | data) > \alpha$; $\alpha = 0.975$
then exclude doses i

4.2.2. Part 2

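### The maximum-sample-size stopping criterion sets Part 2 at about 70 patients, or about 30 per arm, while the plan is about 100 in arms of 40, 30 and 30

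*Protocol*

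**What the plan says.** **Stopping criterion.** Protocol 3.1.5 lists criteria under which dose escalation, dose finding and expansion end. For Part 2 the lead-in reads "each arm of the dose expansion in Part 2 of the study will stop as the applicable following criteria are met". The first criterion is the maximum sample size, printed as about 75 for Part 1, "excluding patients enrolled in biomarker cohorts, and approximately 70 patients in Part 2".

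The SAP prints this criterion twice, with different numbers:
- SAP 4.2.1 has about 75 for Part 1 and "approximately 70 patients in Part 2".
- SAP 2.1.4 has "approximately 50 patients in Part 1" and "approximately 30 patients in each dose arm in Part 2".

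**Planned size.** Protocol 3.1 states "Approximately 100 patients are expected to be enrolled in Part 2"; Protocol 9.3.2 and SAP 2.1 and 5.2 give the same total. By arm, Protocol 3.2.1 says of Arm A "This expansion cohort will enroll approximately 40 patients", and Protocol 3.2.2 and 3.2.3 each say of Arms B and C "This expansion cohort will enroll approximately 30 patients". SAP 2.2.2 and 2.2.3 repeat 40 for Arm A and 30 for Arm B. SAP 2.2.4 gives 30 for Arm C as an upper limit, not an approximate figure. For Part 1, Protocol 3.1, 9.2.2 and 9.3.1 and SAP 2.1 and 5.1 all give about 75.

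**Number of arms.** The opening paragraphs of Protocol 3.2, SAP 2.2 and SAP 4.2.2 speak of two expansion arms, although three are described.

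**The concern.** A maximum that ends accrual cannot sit 30% below the number the plan expects to enrol. Read literally, Part 2 closes at 70 and the plan for 100 is never reached. The criterion is meant to stop each arm but is given as one pooled total, so it does not say which arm closes when 70 is reached. Of the listed criteria, the 6-to-12-patients rule is written for Parts 1A, 1B and 1C and the third concerns finding the MTD. Sample size is therefore the one that clearly bears on Part 2.

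The SAP adds a second conflict, because its two printings disagree with each other and each disagrees with its own sample-size section.

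The objective response rate is a primary Part 2 endpoint, reported by arm with an exact confidence interval, so arm size sets its precision. The CSR also has to set planned against actual enrolment. With several planned sizes in the SAP, a reader cannot tell whether an arm ended at its planned size, under a cap, or because the study was terminated.

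**Working it through.** **1. Reproduce the planned total.** From Protocol 3.2.1, 3.2.2 and 3.2.3: 40 + 30 + 30 = 100. This matches the 100 in Protocol 3.1 and 9.3.2 and SAP 2.1 and 5.2.

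**2. The cap of 70 (Protocol 3.1.5, SAP 4.2.1).** 100 − 70 = 30 patients; 30/100 = 30%. Arms A and B alone give 40 + 30 = 70, so the figure is consistent with text that was not updated when Arm C was added.

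**3. The cap of 30 per arm (SAP 2.1.4).**
- Arm A: 40 − 30 = 10; 10/40 = 25%.
- Arms B and C: no difference.
- Implied total: 3 × 30 = 90, against 100. With the two-arm wording of SAP 2.2 it would be 2 × 30 = 60.

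**4. Part 1 (SAP 2.1.4).** 75 − 50 = 25; 25/75 = 33%.

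**5. Precision, for the SAP 2.1.4 discrepancy in Arm A only.** The 95% exact (Clopper-Pearson) limits for x responders in n are the 0.025 quantile of Beta(x, n − x + 1) and the 0.975 quantile of Beta(x + 1, n − x). The observed response rates are assumptions, because the documents show none.

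| Assumed ORR | n = 40 | n = 30 | Increase in width (points) |
|---|---|---|---|
| 10% | 2.8–23.7% | 2.1–26.5% | 3.55 |
| 20% | 9.1–35.6% | 7.7–38.6% | 4.26 |
| 30% | 16.6–46.5% | 14.7–49.4% | 4.69 |
| 40% | 24.9–56.7% | 22.7–59.4% | 4.93 |
| 50% | 33.8–66.2% | 31.3–68.7% | 5.01 |

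The last column uses unrounded limits. The table takes Arm A alone, as SAP Table 3 reports by arm; combining it with Part 1B patients, as Protocol 9.2.2 allows, would change both sample sizes.

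**6. What cannot be computed.** No precision figure is possible for the cap of 70, because the rule does not say which arm closes. Power cannot be checked: Protocol 9.3.2 gives a one-sided 0.1 error rate and at least 80% power, but the benchmark rates are redacted.

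**The case against.** The strongest reply is that nothing turns on this now. SAP 4.1 and 9.1 plan no hypothesis tests, and SAP 3 plans no formal interim analysis. No visible estimator or analysis set uses 70, 50 or 30 per arm, since SAP Table 3 analyses patients as enrolled. Protocol Appendix 8 dates the termination decision to 07 September 2022, and SAP version 4.0 is dated 23 March 2023, shortly before the primary completion date of about 5 April 2023.

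The intended size can also be recovered. The sample-size sections of both documents say 100, and the amendment history records a change from 70 to 100 in Protocol 3.1 and 9.3.2 when Arm C was added. The 50 for Part 1 stands alone against 75 elsewhere. The 30 per arm is correct for Arms B and C. The interval figures assume that a design summary in the SAP overrides both Protocol 3.2.1 and SAP 2.2.2, and they amount to only about 1.8 to 2.5 points per side.

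Most of this stands as a limit on the consequences. Enrolment and planned analyses are unaffected, the interval widths illustrate only the Arm A discrepancy, and the Arm C wording has no numerical effect. It does not remove the error. The criterion is a stopping rule, it is wrong in current text of both documents, and 'approximately' does not absorb gaps of 25% to 33%. Being able to infer the right number from other sections is a reason to correct the rule, not to leave it.

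**Conclusion.** The concern holds. The Part 2 threshold is wrong as written in Protocol 3.1.5 and SAP 4.2.1 (70 against 100, 30% short). SAP 2.1.4 is wrong for Arm A (30 against 40, 25% short) and for Part 1 (50 against 75, 33% short), so the SAP contradicts itself. If Arm A had stopped at 30, its exact 95% interval for response would be about 3.5 to 5 points wider in total, for assumed observed rates of 10% to 50%.

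This conclusion takes 100, split 40, 30 and 30, as the intended size, because the arm sizes and four separate statements of the total agree on it. It makes no claim of lost power. It should be corrected so that the SAP and CSR carry a single planned size.

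**What to change.** - **SAP 4.2.1:** give the Part 2 maximum as about 100, split as about 40 in Arm A, 30 in Arm B and 30 in Arm C.
- **SAP 2.1.4:** use the same per-arm numbers, and 75 for Part 1.
- **SAP 2.2 and 4.2.2:** refer to three expansion arms.
- **SAP 2.2.4:** align the Arm C wording with Protocol 3.2.3.
- **Protocol 3.1.5 and 3.2:** make the matching changes if the protocol is amended again.

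If no further amendment is planned, it is enough to correct the SAP and to report in the CSR the one planned size per arm beside the number actually enrolled. The cost is wording only: these are figures already stated elsewhere, and no patients are added.
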